[figure not shown]

**LIST OF ABBREVIATIONS AND RELEVANT DEFINITIONS**

ABR	General Assessment and Registration form (ABR form), the application form that is required for submission to the accredited Ethics Committee; in Dutch: Algemeen Beoordelings- en Registratieformulier (ABR-formulier)
AE	Adverse Event
AED	Anti-epileptic drugs
ALE	Adverse local event
BED	Biologically effective dose
CCMO	Central Committee on Research Involving Human Subjects; in Dutch: Centrale Commissie Mensgebonden Onderzoek
CTCAE	Common Terminology Criteria for Adverse Events
CTV	Clinical target volume
CV	Curriculum Vitae
DSMB	Data Safety Monitoring Board
EORTC	European Organisation for Research and Treatment of Cancer
EPTN	European Particle Therapy Network
EudraCT	European drug regulatory affairs Clinical Trials
Gd	Gadolinium
GCP	Good Clinical Practice
GDPR	General Data Protection Regulation; in Dutch: Algemene Verordening Gegevensbescherming (AVG)
GTV	Gross tumor volume
fSRT	Hypofractionated stereotactic radiotherapy
HRQoL	Health-related quality of life
IADL	Instrumental activities of daily living
IB	Investigator's Brochure
IC	Informed Consent
ICH	International Council for Harmonisation of Technical Requirements for Pharmaceuticals for Human Use
KPS	Karnofsky performance status
LINAC	Linear accelerator
LPRNO	National Platform Radiotherapy and Neuro-oncology in the Netherlands; in Dutch: Landelijk Platform Radiotherapie en Neuro-oncologie

---

METC	Medical research ethics committee (MREC); in Dutch: medisch-ethische toetsingscommissie (METC)
MRI	Magnetic resonance imaging
OAR(s)	Organ(s) at risk
PI	Principal investigator
PTV	Planning target volume
RANO	Response Assessment in Neuro-Oncology
RANO-BM	Response Assessment in Neuro-Oncology Brain Metastases
RLIES	Revised Liverpool Impact of Epilepsy Scale
(S)AE	(Serious) Adverse Event
SRT	Stereotactic radiotherapy
Sponsor	The sponsor is the party that commissions the organization or performance of the research, for example a pharmaceutical company, academic hospital, scientific organization or investigator. A party that provides funding for a study but does not commission it is not regarded as the sponsor, but referred to as a subsidizing party.
SUSAR	Suspected Unexpected Serious Adverse Reaction
UAVG	Dutch Act on Implementation of the General Data Protection Regulation; in Dutch: Uitvoeringswet AVG
V12Gy	Tissue volume receiving a dose of at least 12Gy
WBRT	Whole brain radiotherapy
WHO-PS	World Health Organization performance status
WMO	Medical Research Involving Human Subjects Act; in Dutch: Wet Medisch-wetenschappelijk Onderzoek met Mensen

## SUMMARY

**Rationale:** Stereotactic radiotherapy is one of the most frequently chosen treatment options for brain metastases. There are an increasing number of long term survivors. Brain necrosis (e.g. radionecrosis) is the most important long term side effect of the treatment, occurring in up to 40% of patients, dependent on the size of the metastasis and delivered radiotherapy dose. Retrospective studies have shown that the incidence of radionecrosis, as well as local tumor recurrence, can be decreased with a risk difference of around 20% by administrating fractionated stereotactic radiotherapy (fSRT, e.g. five fractions) over single fraction stereotactic radiotherapy, especially in large brain metastases.

**Objective:** To determine if the incidence of adverse local events (local failure or radionecrosis) can be reduced with more than 20% using fSRT versus SRT in one or three fractions.

**Study design:** Prospective, multicenter, open label, randomized, phase II study with two cohorts.

**Study population:** Patients, 18 years and older, with one or more brain metastases from solid primary tumors diagnosed on a high resolution contrast-enhanced MRI scan referred for stereotactic radiotherapy.

**Intervention (if applicable):** One group is treated with SRT in one or three fractions. The other group is treated with fSRT in five fractions.

**Main study parameters/endpoints:** The main study parameter is the incidence of adverse local event (either local failure or radionecrosis according to RANO) at 2 years post-radiotherapy with respect to baseline.

**Nature and extent of the burden and risks associated with participation, benefit and group relatedness:** The study aims to investigate a different and potentially safer treatment method than the current standard of care. It is unlikely that the risk of adverse events will be increased in the experimental cohort compared to the standard cohort. The additional burden as a result of study participation consists of the following: between two and four additional site visits for treatment in the experimental group; a total of eighteen (facultative) questionnaires spread throughout the follow-up period.

## 1. INTRODUCTION AND RATIONALE

Since publication of the QUARTZ trial, the palliative benefit and indication of whole brain radiotherapy (WBRT) is a matter of debate for patients with brain metastases. After WBRT, patients may suffer from alopecia, fatigue, and there is a risk of neurocognitive dysfunction caused by the elective brain irradiation. In phase III trials, (elective) WBRT has never shown benefit in survival nor health-related quality of life in large cell cancer histologies.

In the last decades, effective alternative treatments for brain metastases have become available. Targeted agents and/or immunotherapy have shown to effectively treat brain metastases in several subtypes of cancer. Stereotactic radiotherapy (SRT) has become widely available, also for multiple brain metastases. SRT has shown to treat brain metastases more effectively with a higher probability of local tumor control than WBRT. Moreover, elective brain irradiation is avoided and thereby side effects of WBRT. Because of publication of the favorable results in terms of local tumor control and median survival of large cohorts of patients with SRT also in patients up to ten brain metastases with low volume disease, several international guidelines (UK NICE guideline, American neurosurgery guideline) state that SRT is also a treatment option for patients with more than three brain metastases. This advice is also stated in the revised Dutch guideline for brain metastases, that radiosurgery is a treatment option for patients up to 10 brain metastases with a maximum individual volume of the brain metastases of 20 cm^3 and a maximum cumulative volume of 30 cm^3. In the current era of personalized medicine, the main question is how to integrate SRT into the multimodality treatment for brain metastases with systemic therapies and surgery. This is complex and decided in the multidisciplinary board.

As clinicians, we observe an increasing number of long term survivors over several years with brain metastases. Brain necrosis or radionecrosis is a long term side effect of SRT which occurs in +/-20% of patients and the incidence may increase up to +/-40% if SRT is combined with immunotherapy. Radionecrosis may cause neurologic symptoms, such as focal neurological deficits, neurocognitive dysfunction and seizures, which require treatment with steroids, bevacizumab, or sometimes even surgery. SRT is mostly delivered with an ablative high radiotherapy dose in a single fraction. In the first millimeters close to the brain metastasis, the healthy brain tissue receives a high dose as well.

In radiotherapy literature, it is known that more fractionated radiotherapy, e.g. hypofractionated radiotherapy (fSRT), may decrease side effects. fSRT means delivering the ablative dose in multiple fractions (f.e. 5 fractions) over several days instead of delivering the ablative dose within half an hour. Recent retrospective studies showed that risk difference of local failure and radionecrosis is almost 30% in larger tumors (>2.5 cm; constituting around

50% of metastases), while the incidence is equivalent in smaller metastases. To achieve a local control of more than 90% after one year, it is important to deliver a cumulative biologically effective dose (BED) of at least 50 Gy. 35 Gy in 5 fractions results in a BED of more than 50Gy. Another potential benefit of fSRT over SRT in one or three fractions is better induction of an abscopal effect. SRT in one or three fractions results in massive tumor necrosis. fSRT may result in more regulated cell death: apoptosis, with better antigen presentation of dying tumor cells. It is hypothesized that this may subsequently result in better activation of the immune cells against the cancer and better control of micrometastases outside the irradiation field. Several studies are ongoing in which SRT is combined with immunotherapy to increase systemic tumor control and thereby improve survival.

## 2. OBJECTIVES

Primary Objective: To determine if the percentage of adverse local events (either local failure or radionecrosis) can be reduced by using fSRT versus SRT in one or three fractions 2 years post-SRT.

Secondary Objective(s): To investigate if fSRT provides better quality of life and lower incidence of epilepsy versus SRT in one or three fractions. Additionally, to estimate overall survival as well as the cumulative incidence of local failure or radionecrosis with death as competing risk.

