#### 8.1.2 Secondary study parameters/endpoints

- Survival time/survival at 2 years post-SRT
- Incidence of symptomatic radionecrosis
- Incidence of symptomatic local failure
- Incidence of salvage treatments at 2 years post-SRT
- Distant brain recurrences at 2 years post-SRT
- Dose dexamethasone at baseline, 3 months after radiotherapy and thereafter every three months until 2 years
- Anti-epileptic drug (AED) use
- Bevacizumab use
- Grade 2 or more toxicity (CTCAE v5.0)
  - Alopecia, cognitive symptoms, fatigue, dysphasia, hearing loss, visual impairment, generalized muscle weakness

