#### 8.1.3 Other study parameters

Facultative endpoints:

- HRQoL (measured with EORTC QLQ-C30 and QLQ-BN20) at baseline, 3, 6, 12, 18 and 24 months after radiotherapy
- IADL (measured with EQ-5D 5L) at baseline, 3, 6, 12, 18 and 24 months after radiotherapy

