### 9.2 AEs, SAEs and SUSARs

#### 9.2.1 Adverse events (AEs)

Adverse events are defined as any undesirable experience occurring to a subject during the study, whether or not considered related to the experimental intervention. All adverse events reported spontaneously by the subject or observed by the investigator or his staff will be recorded in the medical record of the patient.

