#### 9.2.2 Serious adverse events (SAEs)

A serious adverse event is any untoward medical occurrence or effect that

- results in death;
- is life threatening (at the time of the event);
- requires hospitalization or prolongation of existing inpatients' hospitalization;
- results in persistent or significant disability or incapacity;
- is a congenital anomaly or birth defect; or
- any other important medical event that did not result in any of the outcomes listed above due to medical or surgical intervention but could have been based upon appropriate judgement by the investigator.

An elective hospital admission will not be considered as a serious adverse event.

The investigator shall report serious adverse events to [[contact]](mailto:[contact]) without undue delay after obtaining knowledge of the events, unless, for certain serious adverse events, the protocol provides that no immediate reporting is required.

Adverse experiences of a serious and unexpected nature, whether or not related to the cerebral radiotherapy, must be reported immediately. Adverse events that are

unexpected, should be reported if there is a possibility that it could be related to the administration of the radiotherapy.

The investigator will report all SAEs to the sponsor without undue delay after obtaining knowledge of the events, except for the following SAEs: epilepsy, deterioration of existing neurologic impairment after the radiotherapy, alopecia, fatigue, headache, and taste disorders.

The sponsor will report the unexpected SAEs through the web portal *ToetsingOnline* to the accredited METC that approved the protocol, within 7 days of first knowledge for SAEs that result in death or are life threatening followed by a period of maximum of 8 days to complete the initial preliminary report. All other unexpected SAEs will be reported within a period of maximum 15 days after the sponsor has first knowledge of the serious adverse events.

Patients with brain metastases generally have a poor life expectancy of around 3-12 months. Therefore, a significant proportion of patients is expected to die within the study duration of 1 year after SRT.

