Expected SAEs are hospitalization or death by progression of both extracranial and intracranial cancer. Moreover, patients are treated with systemic therapy, and may be hospitalized or die because of complications of the systemic therapy, such as secondary infections. Furthermore, a proportion of patient will have severe neurologic impairment and epilepsy, because of intracranial cancer progression despite radiotherapy. These expected SAEs will be reported every half year in a line listing.

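### The secondary objective on epilepsy incidence has no seizure endpoint, assessment or analysis behind it; anti-epileptic drug use is the only planned epilepsy measure

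*Protocol*

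**What the plan says.** Section 2 gives as a secondary objective: "To investigate if fSRT provides better quality of life and lower incidence of epilepsy versus SRT in one or three fractions".

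Section 8.1.2 lists the secondary endpoints. The epilepsy-specific one is "Anti-epileptic drug (AED) use". The toxicity endpoint is grade 2 or higher under CTCAE v5.0, followed by these terms: "Alopecia, cognitive symptoms, fatigue, dysphasia, hearing loss, visual impairment, generalized muscle weakness". The same list includes the incidence of symptomatic radionecrosis and of symptomatic local failure.

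Section 8.1.3 adds facultative questionnaires: "HRQoL (measured with EORTC QLQ-C30 and QLQ-BN20) at baseline, 3, 6, 12, 18 and 24 months after radiotherapy", and the EQ-5D 5L for daily activities. The abbreviation list defines an epilepsy instrument, the "Revised Liverpool Impact of Epilepsy Scale", which no endpoint, schedule or analysis section uses.

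Table 1 and section 8.3.10 schedule toxicity and AED use every three months to two years. Section 10.2 plans mixed modelling of AED use.

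On safety, section 9.2.1 says that adverse events "will be recorded in the medical record of the patient". Section 9.2.2 requires investigators to report SAEs promptly to the sponsor, "except for the following SAEs: epilepsy, deterioration of existing neurologic impairment after the radiotherapy" and several other conditions. The same section then describes expected SAEs that go into a half-yearly line listing. It names epilepsy there as occurring "because of intracranial cancer progression despite radiotherapy".

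**The concern.** The objective asks how often epilepsy occurs in each arm. The planned variable records who takes a drug. The two can differ in both directions: a patient already on an AED at baseline may have seizures and show no change in drug use, and a patient given an AED without a seizure looks like a case.

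This matters more here than for an incidental side effect. Section 1 names seizures among the symptoms of radionecrosis, and radionecrosis is half of the composite that the trial hopes to reduce. A difference in seizures would be a patient-level consequence of the effect under test. If seizures are not collected prospectively, the report will either be silent on a stated objective or present a prescribing comparison as if it were an incidence comparison. Going back to the charts afterwards, across several centres in an open-label trial, would give incomplete data that are prone to ascertainment bias.

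**Working it through.** The protocol gives no epilepsy rate, effect size or power, so there is no figure of its own to reproduce on this point. Its only power figure (section 4.4: 59 per arm, 30% versus 10%, power 0.8051, actual alpha 0.0507) is confirmed by exact binomial enumeration of the pooled Z test. It concerns the primary endpoint and has no bearing here. The check consists of following the objective through the document.

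| Step | Where | What is there for epilepsy |
|---|---|---|
| Objective | Section 2 | Between-arm comparison of incidence |
| Primary endpoint | 8.1.1 | Nothing |
| Secondary endpoints | 8.1.2 | AED use; no seizure or epilepsy endpoint, no case definition |
| Named toxicity terms | 8.1.2 | 7 terms, none of them seizure |
| Facultative endpoints | 8.1.3 | Quality of life and daily activities; no epilepsy scale |
| Baseline characteristics | Table 1 | No seizure or epilepsy history; AED use only |
| Follow-up at 3, 6, 9, 12, 15, 18, 21 and 24 months (8 visits) | Table 1, 8.3.10 | AED use and CTCAE toxicity; no seizure row |
| Analysis | 10.2 | Mixed model of AED use; none of epilepsy incidence |

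**Could another scheduled item stand in?**

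- *Symptomatic radionecrosis or local failure.* Table 1 has this at all eight visits. A seizure attributed to radionecrosis would make the radionecrosis symptomatic and so be counted. But the item does not say which symptom occurred, so seizures cannot be separated from focal deficits or cognitive change. Seizures with another cause are not counted.
- *CTCAE toxicity.* The schedule does not expressly limit the form to the seven terms, so a seizure may be written down. The endpoint names seven terms without it, so complete capture cannot be assumed.
- *Questionnaires.* They are optional, are given at baseline and five follow-up times, and are assigned to quality of life and daily activities.

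**How much could the proxy miss?** The documents do not say how many patients take an AED at baseline. Suppose, as an assumption, that 10% to 30% do, and that use is stored as yes or no. With 59 per arm, that is 59 × 0.10 = 5.9 to 59 × 0.30 = 17.7, or about 6 to 18 patients per arm in whom a later seizure need not alter the recorded variable. The conclusion does not depend on this range.

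**Safety reporting.** The exception in section 9.2.2 stands in a sentence about prompt reporting. The later paragraph places epilepsy in the half-yearly listing but ties it to intracranial progression. Serious epilepsy caused by radionecrosis falls under the exception and is not clearly within the listing.

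**The case against.** The strongest defence is that seizures are not invisible to this trial. Symptomatic radionecrosis is a named endpoint assessed at every follow-up visit. The CTCAE form is not stated to be closed. Adverse events enter the medical record, which section 11.2 allows to be reviewed for trial purposes, and section 12.4 includes serious adverse events in the annual progress report. The case report forms are not shown. AED use is analysed with repeated measures and might be recorded in more detail than yes or no. The objective is also only half of one unpowered secondary aim in a phase II trial of about 130 patients.

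Much of this stands, and it rules out stronger readings. A reader might infer that epilepsy is exempt from SAE reporting altogether, that a seizure from radionecrosis has no way into the trial data, or that nothing but AED use is recorded. The documents do not support these. The exception can be read as removing prompt reporting only, the listing covers progression-related epilepsy, and several items may pick up a seizure incidentally.

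The defence does not supply an epilepsy incidence. None of these routes gives a defined event, a date and a baseline status for every patient, and none is tied to an analysis. Nor can this be left to the analysis plan, because what is collected at each visit has to be fixed in the protocol.

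**Conclusion.** The point holds: a stated comparative objective has no matching endpoint, scheduled seizure assessment or analysis, and AED use is a proxy for prescribing. The objective cannot be answered from the assessments as specified. That is narrower than saying seizures go unrecorded, which the documents do not show.

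The primary endpoint and the main conclusion are untouched, so this should be corrected but does not threaten the trial. No numerical bias can be derived, because the protocol gives no epilepsy or AED rates; the 6 to 18 patients per arm above rest on an assumed range and on yes/no recording. The safety-reporting issue is limited to two statements within section 9.2.2 that do not make clear how serious epilepsy from causes other than progression is reported.

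**What to change.** 1. Add seizure to section 8.1.2 and Table 1, with CTCAE v5.0 grade and date of first event, at baseline and the eight existing three-monthly visits. Record seizure history at baseline so that new onset can be told from pre-existing epilepsy.
2. In section 10.2, compare the cumulative incidence of first post-treatment seizure between arms with death as a competing event, as is already planned for adverse local events. Keep AED use as supporting data.
3. If seizures will not be collected, restate the objective in section 2 as a comparison of AED use.
4. Separately, reconcile the SAE exception and the line-listing paragraph in section 9.2.2, so that the reporting route for serious epilepsy and neurologic deterioration is clear whatever the cause.
5. Use the epilepsy scale in the abbreviation list or remove it.

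The cost is one extra case report form item at visits that already grade toxicity, a baseline history question, and a few more lines in an existing listing.

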### 3. STUDY DESIGN

The study is a prospective randomized cohort study with two study cohorts. Patients are allocated to a study cohort by randomization. The follow-up will be two years. The study will take place in a multicenter clinical setting.

Patients from the two study cohorts will receive a different fractionation treatment schedule. Patients in the standard cohort will receive SRT in one or three fractions according to the Dutch guideline (consensus Landelijk Platform Radiotherapie en Neuro-oncologie; LPRNO), while patients in the experimental cohort will receive fSRT in five fractions.

The planned duration is as follows:

Data collection: March 2022-March 2027 (3 years for patient inclusion, 2 years follow-up)

Statistical analyses: March 2027

Writing article: April 2027-June 2027

NB: these dates are an estimate and are dependent on several factors, such as approval from the ethics and research commissions.

## 4. STUDY POPULATION

### 4.1 Population (base)

Patients (≥18 years old) with one or more brain metastases from solid primary tumors diagnosed on a high resolution contrast-enhanced MRI scan referred for SRT in Dutch hospitals.

### 4.3 Exclusion criteria

A potential subject who meets any of the following criteria will be excluded from participation in this study:

- Contra-indication for MRI scan
- Primary tumor of small cell lung cancer, germinoma or lymphoma
- Prior whole brain radiotherapy or SRT on the current target brain metastases (BM) (in field re-irradiation; salvage SRT of non-irradiated BM allowed if radiation dose from previous irradiation in current target field is <1.0 Gy)
- Presence of leptomeningeal metastases
- Previous inclusion in the SAFESTEREO study

### 4.4 Sample size calculation

Standard cohort: Mean risk of local failure or radionecrosis 1 year = 30%

Experimental cohort: Mean risk of local failure or radionecrosis experimental arm @ 1 year = 10%

Enrollment ratio standard vs experimental cohort 1:1

Alpha = 0.05

Power=0.8

Sample size standard arm n=59

Sample size experimental arm n=59

Minimum number of patients required for the study: 118

Number of patients including additional 10% to account for missing data: 130

These number were based on the following power analysis and were calculated with PASS® software (NCSS Statistical Software):

The results are based on the exact binomial test:

Numeric results of tests based on the difference: P1 - P2

H0: P1 - P2 = 0. H1: P1 - P2 = D1 ≠ 0. Test Statistic: Z test with pooled variance.

Power	Sample size group 1 (N1)	Sample size group 2 (N2)	Prop H1 Group 1 (P1)	Prop Group 2 (P2)	Diff if H0 (D0)	Diff if H1 (D1)	Target alpha	Actual alpha	Beta
0.8051	59	59	0.3000	0.1000	0.000	0.200	0.0500	0.0507	0.1949

Note: exact results based on the binomial were only calculated when both N1 and N2 were less than 100.

The total number of patients with brain metastases treated at the department of radiotherapy in our hospital in 2019 was around 150, of whom an estimated 135 would have been eligible for inclusion. Therefore, a 3-year period (as mentioned in paragraph 3) should be sufficient to include enough patients.

